Participants:

[figure not shown]
Inclusion Criteria: We will enroll 60 veterans with PTSD. To be eligible for the study, participants must meet current DSM-V diagnostic criteria for PTSD (American Psychiatric Association, 2013). PTSD will be established by interview using the Clinician Administered Posttraumatic Stress Disorder Scale for the DSM-V (CAPS-5; Weathers et al., 2013a). Participants must also indicate current difficulties with anger and aggression as indicated by a score of 20 or higher on the trait anger scale of the State Trait Anger Expression Inventory-2 (STAXI-2, Spielberger, 1999), indicating moderate to severe anger problems. Veterans from all eras will be eligible to participate.

Exclusion Criteria: Participants with a current diagnosis of bipolar disorder, psychotic disorder, or current substance use disorder with severe symptoms. Participants also must not have a seizure disorder and must not be taking any medications that would affect cognition or behavior on the aggression task, including pain medication, benzodiazepines, or antipsychotics. Participants also must not have a positive drug (e.g., amphetamine, opiates, and cocaine) or alcohol urine screen at the post-treatment session (see below), as these substances could affect performance on the study tasks implemented at that session. Finally, participants must not currently be receiving concurrent individual therapy or group therapy focused on anger and aggression and must not currently be participating in the modified TREC group offered at the West Haven VA (WHVA).

Research Design and Methods

For an overview of the time line for study procedures, see Figure 2.

Figure 2. Timeline of Study Procedures

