| Diagnostic Assessments | | | | | |
| Clinician Administered PTSD Scale for DSM-V: Past-Month Version (CAPS-5) | X | | | | |
| Structured Clinical Interview for DSM-5 Disorders-Research Version (SCID-5-RV) | X | | | | |
| Life Events Checklist-5 (LEC) | X | | | | |
| Primary Outcome Measures: Self-Report | | | | | |
| State Trait Anger Expression Inventory-2 (STAXI-2) | X | X | X | X | X |
| Buss-Perry Aggression Questionnaire (BPAQ) | X | X | X | X | X |
| Primary Outcome Measure: Experimental | | | | | |
| Taylor Reaction Time Task (TRT) | | | | X | |
| Secondary Outcome Measures | | | | | |
| Physiological Reactivity: Heart Rate, Skin Conductance | | | | X | |
| Emotion Regulation: State Difficulties in Emotion Regulation Scale (DERS-S) | | | | X | |
| Exploratory Outcome Measures | | | | | |
| Five Facet Mindfulness Questionnaire (FFMQ) | X | X | X | X | X |
| PTSD Checklist for the DSM-V (PCL-5) | X | X | X | X | X |
| Quantity-Frequency Variability Index (QFI) | X | X | X | X | X |
| Alcohol Dependency Scale (ADS) | X | X | X | X | X |

Baseline Session:

(a) PTSD, other psychiatric disorders, anger and aggression:

The DSM-V criteria for PTSD will be established using the Clinician Administered PTSD Scale: Past-Month Version (CAPS-5, Weathers et al., 2013a). The CAPS-5 will be used to confirm DSM-V PTSD diagnosis and to provide a continuous measure of PTSD severity (CAPS-5 total score). To facilitate the administration of the CAPS, participants will also complete the Life Events Checklist-5 (LEC; Weathers et al., 2013b), which is a self-report questionnaire used to assess the extent to which individuals experienced any of 17 different stressful or difficult life events (e.g., combat exposure, natural disaster, fire or explosion).

Participants will be assessed for psychiatric disorders at the baseline session using the Structured Clinical Interview for DSM-5 Disorders – Research Version (SCID-5-RV, First et al.,

2014). The information from the SCID will be used to exclude participants with severe psychiatric disorders (e.g., schizophrenia or bipolar disorder).

(b) Battery of Self-Report Questionnaires: Participants will also complete a battery of self-report questionnaires including assessments measuring anger and aggression, in addition to trait mindfulness, PTSD, and alcohol use:

- State Trait Anger Expression Inventory-2 (STAXI-2, Spielberger, 1999)
- Buss-Perry Aggression Questionnaire (BPAG; Buss and Perry, 1992)

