Secondary Aim 1, Hypothesis 1.2: Within the MBSR group, decreases in physiological reactivity and increases in emotion regulation will be associated with decreases in aggression on the TRT. Pearson product moment correlations will be calculated to examine the association between changes in HR, SC, and emotion regulation and the TRT responses (i.e., mean shock level across the TRT and total number of “20” shocks chosen on the TRT).

Sample Size and Power Considerations

Although the proposed sample size may not be sufficient in establishing statistical significance but rather a pattern of results that suggest promising effects across anger outcomes, it is important to emphasize that the fundamental purpose of the pilot trial is to provide information for the planning of a future large scale clinical trial examining the efficacy of MBSR in decreasing anger and aggression in veterans with PTSD and examining additional mechanisms of action (i.e., behavioral, cognitive, social, biological) that lead to behavior change. To that end, the pilot RCT data will be used in power calculations to calculate the sample size for a later full-scale RCT examining MBSR for anger and aggression for veterans with PTSD.

Effect sizes for determining the sample size for the larger RCT will be calculated based on differences between the baseline and post-treatment scores on the self-report measures of

anger and aggression (STAXI-2, BPAQ), as well as the difference scores between the physiological measures (i.e., HR and SC) and emotion regulation obtained during the experimental portion of the post-treatment session. Comparisons will be made using a two-sample t-test. Due to the possibility that estimation of effect sizes based on pilot studies may be inaccurate (Kraemer et al., 2006), we will implement procedures recommended for improved characterization of effect sizes derived from pilot studies (Thabane et al., 2010). These include close consultation with clinicians who have used the treatment (i.e., [name]), and accounting for the effect size uncertainty by constructing confidence intervals around the observed effect size.

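### The pilot's effect sizes for planning the next trial use unadjusted change scores and a t-test that ignores therapy groups, and they leave out the TRT, a primary outcome

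*Combined protocol and SAP*

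**What the plan says.** Under Sample Size and Power Considerations the plan concedes that the sample may be too small for statistical significance and puts the pilot's value in planning: "the pilot RCT data will be used in power calculations to calculate the sample size for a later full-scale RCT". Two kinds of measure supply the effect sizes. The self-report part rests on "differences between the baseline and post-treatment scores on the self-report measures". The full list of measures reads "anger and aggression (STAXI-2, BPAQ), as well as the difference scores between the physiological measures (i.e., HR and SC) and emotion regulation obtained" in the post-treatment session. The method is one sentence: "Comparisons will be made using a two-sample t-test". Uncertainty is to be handled by consulting clinicians and by "accounting for the effect size uncertainty by constructing confidence intervals around the observed effect size".

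Three other places bear on this:

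- Table 1 (Schedule of Assessments) puts the TRT under "Primary Outcome Measure: Experimental", measured at post-treatment only. Data Analyses tests its two measures, mean shock level and number of '20' shocks, under Primary Aim 1, Hypothesis 1.2.
- Data Analyses specifies mixed models for STAXI-2 and BPAQ, with treatment, time and their interaction as fixed effects and therapy group as a random effect. It also requires a yes/no medication covariate in every analysis.
- The inclusion criteria require "a score of 20 or higher on the trait anger scale" of the STAXI-2. The trait-anger baseline is therefore truncated by selection.

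**The concern.** By the plan's own account, effect sizes and their intervals are the pilot's main product. Three features weaken them.

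1. An unadjusted change score subtracts the whole baseline value, although baseline normally predicts the later score with a slope below 1. The extra subtraction adds noise that a baseline covariate would remove.
2. A two-sample t-test treats participants as independent. They are treated in groups of 6, and the main analysis models that grouping. The plan does have an intra-class correlation step, but it adjusts the later trial's sample size, not the pilot's interval. The t-test also cannot carry the medication covariate.
3. The list includes secondary outcomes (heart rate, skin conductance, emotion regulation) but skips a primary one, the TRT. The background section itself criticises heavy reliance on self-report and argues for laboratory tasks.

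At stake is how well, and on which outcomes, the next trial can be sized.

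**Working it through.** **Inputs.** The plan says "We will enroll 60 veterans with PTSD". Randomization Procedures gives groups of 6, so about 10 groups. I assume 30 participants and 5 groups per arm, because the ratio is not stated. No r, SD, effect size or intra-class correlation is given, so there is no figure of the plan's own to reproduce. Ranges are shown instead.

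**Step 1: precision, equal baseline and post-treatment variances (SD = 1).**

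- Variance of change: 2(1 − r).
- Residual variance after baseline adjustment: 1 − r².
- Excess variance of change: 2(1 − r)/(1 − r²) − 1 = 2/(1 + r) − 1.

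The 95% half-width for the arm difference is t × √(variance × 2/30). The adjusted variance also carries the finite-sample factor 1 + 1/56.

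| Assumed r | Var(change) | Var(adjusted) | Excess | Half-width, change | Half-width, adjusted |
|---|---|---|---|---|---|
| 0.3 | 1.40 | 0.91 | 54% | 0.61 | 0.50 |
| 0.5 | 1.00 | 0.75 | 33% | 0.52 | 0.45 |
| 0.7 | 0.60 | 0.51 | 18% | 0.40 | 0.37 |
| 0.9 | 0.20 | 0.19 | 5% | 0.231 | 0.227 |

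Simulation with 30 per arm (6,000 trials per r) gave adjusted-to-change variance ratios of 0.67, 0.77, 0.88 and 0.96. The formula gives 0.65, 0.75, 0.85 and 0.95 before the finite-sample factor.

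**Step 2: trait anger, truncated at 20.** Assume an untruncated mean of 20 to 24, SD 6, and post = r × baseline + error. Let v be the truncated baseline variance as a fraction of the untruncated variance. The change variance is then (1 − r)²v + (1 − r²), so the excess is v(1 − r)/(1 + r).

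- Mean 20, v = 0.363: 0.363 × 0.333 = 12% at r = 0.5; 0.363 × 0.176 = 6% at r = 0.7.
- Mean 24, v = 0.533: 0.533 × 0.333 = 18% at r = 0.5; 0.533 × 0.176 = 9% at r = 0.7.

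The range is about 6% to 18%.

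**Step 3: the interval.** With 5 groups of 6 per arm, the variance of an arm difference is inflated by 1 + 5ρ. Simulated coverage of a nominal 95% t-test interval was 94.5%, 92.0%, 88.8% and 85.8% at assumed ρ of 0.01, 0.05, 0.10 and 0.15.

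**Step 4: which measures are affected.** Steps 1 and 2 concern STAXI-2 and BPAQ only. Heart rate, skin conductance and emotion regulation are taken only at the post-treatment session, so their differences are within-session and there is no pre-randomisation value to adjust for. The TRT is also post-only and needs a post-treatment between-arm effect, not a change score.

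**Step 5: whether the planned mixed model already adjusts.** It does not. In that model baseline is one of the outcome times and the treatment effect at baseline is free. With complete data and time as categories, its baseline-to-post interaction contrast is the difference in mean change, which is the same estimate as the t-test's.

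**The case against.** The strongest reply is that little is lost. The change-score difference is unbiased under randomisation, the plan admits that pilot effect sizes may be inaccurate and requires intervals, and with about 30 per arm the estimate is imprecise either way: at r = 0.7 the half-width only falls from 0.40 to 0.37. If the next trial adjusts for baseline, a sample size based on change scores errs on the safe side. All of this stands, and it limits the point to a gain in precision. It does not answer the omission of therapy group from the interval, because the intervals are the plan's chosen safeguard.

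Three stronger readings are tempting, and the documents do not support them.

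- *The next trial could not be sized on the TRT.* Hypothesis 1.2 already compares both TRT measures between arms, so the information will exist. The gap is that the sizing plan does not commit to reporting it. Nor does the plan say that the next trial will use the TRT.
- *Selection on baseline, or chance imbalance, biases the effect size.* Regression to the mean affects both arms equally in expectation. Imbalance is not a second harm on top of the lost precision: 2(1 − r) = (1 − r²) + (1 − r)², and the last term is both the imbalance contribution and the excess variance. For trait anger its typical size is also modest. At r = 0.5 it is 0.5 × √(2/30) × √v, or 0.08 to 0.09 SD for v of 0.363 to 0.533.
- *Using the planned mixed model would cure it.* As written it would not (Step 5).

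**Conclusion.** The point holds as an improvement in precision and completeness, not as a finding of bias. The self-report effect sizes are noisier than they need be. The excess variance is about 18% to 54% for r between 0.7 and 0.3 with equal variances, and about 5% at r = 0.9. For trait anger it is about 6% to 18% under the truncation assumptions. These figures rest on assumed correlations, means and SDs, since the documents give none. The t-test interval is too narrow if outcomes cluster by therapy group; the amount depends on an unstated intra-class correlation. The absence of both TRT measures from the effect-size list needs no assumption: it is an inconsistency between Sample Size and Power Considerations on one side and Table 1 and Hypothesis 1.2 on the other.

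**What to change.** In Sample Size and Power Considerations:

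1. Replace the change-score t-test for STAXI-2 and BPAQ with post-treatment between-arm differences that have the baseline score as a covariate. This can be ANCOVA, or a mixed model with baseline as a covariate or with the arm means at baseline constrained equal. Say which, because the model now in Data Analyses does none of these.
2. Keep the random therapy-group effect and the medication covariate. Divide by a stated SD and give confidence intervals. Also report the SD, r and intra-class correlation, which the next trial's calculation will need.
3. Add mean shock level and number of '20' shocks as post-treatment between-arm effects with intervals.

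The cost is analysis-plan wording. The schedule already collects all the data.

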Trauma Scripting Procedure. After completing the diagnostic interviews (CAPS-5/SCID-5-RV), eligible participants will participate in a trauma-script development procedure as part of a well-validated, script-driven trauma imagery task (Pitman et al., 1987). For this procedure, participants will be asked to identify their most traumatic experience. If they identify more than one event, they will be asked to choose the one that they consider the most distressing. They will first be asked to describe the experience in writing using a script preparation form and then will be asked to indicate which of several different subjective visceral and muscular reactions (e.g., heart beating slower/faster, feeling sweaty, stomach in knots, feeling warm, hands trembling, tension in arms, nausea) may have accompanied the experience. Participants’ written responses will then be reviewed and they will be asked to clarify or expand on the details if necessary. After the session, a script lasting approximately 60 seconds in duration will be composed that portrays the traumatic experience in the second person, present tense, and incorporates the different visceral or muscular reactions. The script will then be audio recorded for playback

during the experimental portion of the post-treatment session. A research assistant (who will be named later upon being hired) will read the narrative scripts to be audio-recorded.

During this baseline session, participants will also complete a battery of self-report questionnaires (see below for full details) to assess baseline levels of anger and aggression.

Randomization Procedures. After participants have completed the Baseline Screening and Evaluation Session they will be randomized to either the TREC group or the MBSR group. To decrease the amount of time participants have to wait before starting group treatment, randomization will be implemented at the group level. That is, after 6 participants are recruited, they will be randomly assigned using urn randomization procedures, to either the TREC group or the MBSR group.

Post-treatment Session: After all participants have completed their assigned interventions (TREC or MBSR) they will be scheduled for the post-treatment session to be held in the biological studies laboratory at the WHVA. At this session, all participants will complete a battery of self-report questionnaires to assess post-treatment levels of anger and aggression (see below).

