Primary Aim 1 Hypothesis 1.1: Participants assigned to MBSR will report decreased levels of self-reported anger and aggression at post-treatment and at the 3-month follow up compared to those assigned to the TREC group. Scores on the State Trait Anger Expression Inventory-2 and the Buss-Perry Aggression Questionnaire will be used as the primary outcome variables for self-report anger and aggression. Intent-to-treat analyses will be conducted for these outcomes, which will be examined separately. Bonferroni adjustments will be implemented to control for Type 1 error. These data will be analyzed using mixed effects models with treatment, time, and treatment x time interaction as fixed effects. Subject will be the clustering factor and it will be nested within therapy group which will also be considered random. Different variance-covariance structures will be considered and the best one selected based on Schwartz’ Bayesian Information Criterion (BIC). Mixed effects models are the preferred method for analyses of such data as they use all available data on an individual, give unbiased results under general missing data assumptions and provide flexibility in modeling the correlation structure within subject. Significant interactions will be examined further using post-hoc tests.

Primary Aim 1, Hypothesis 1.2: Participants assigned to MBSR will exhibit lower levels of anger and aggression on the TRT compared to those assigned to the TREC group. Mixed effects models will be used to compare the TREC group to the MBSR group on responses on the TRT: (1) mean shock level across the TRT, and (2) total number of “20” shocks chosen on the TRT following the same strategy as for primary aim 1 hypothesis 1.1.

Secondary Aim 1, Hypothesis 1.1: Those assigned to MBSR will exhibit significant decreases in HR and SCL and increases in emotion regulation compared to those assigned to the TREC group. Mixed effects models will be used to compare the TREC group to the MBSR group on physiological variables (HR, SCL) and emotion regulation (DERS-S) following the same strategy as for primary aim 1, hypothesis 1.1.

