Due to the nature of group treatment, additional considerations related to sample size will need to be considered given that a portion of the variance in treatment effects will be accounted for by clustering of effects within a particular group. Clustering group effects can be measured by an intra-class correlation ρ , which is defined as the ratio of variance due to the clustering variable relative to the total variance (cluster and error) (Schnurr et al., 2001). Once ρ has been determined, the adjusted sample size can be determined using the following formula: $m = n * N / (1 + (n - 1) \rho)$, where m is the effective number of independent observations after accounting for interclass correlation; n is the number of repeated measures per group; and N is the base sample size needed to detect the effect.

References:

- American Psychiatric Association (2013). *Diagnostic and statistical manual of mental disorders* (5th ed.) Arlington, VA: American Psychiatric Publishing.
- Anderson, C.A., & Bushman, B.J. (1997). External validity of 'trivial' experiments: The case of laboratory aggression. *Review of General Psychology*, 1, 19-41.
- Anderson, C.A., & Bushman, B.J. (2001). Effects of violent video games on aggressive behavior, aggressive cognition, aggressive affect, physiological arousal, and prosocial behavior: A meta-analytic review of the scientific literature. *Psychological Science*, 12, 353-359.
- Baer, R.A. (2003). Mindfulness training as a clinical intervention. *Clinical Psychology: Science and Practice*, 10, 125-143.
- Ben-Porath, D.D. & Taylor, S.P. (2002). The effects of diazepam (valium) and aggressive disposition on human aggression: An experimental investigation. *Addictive Behavior*, 27, 167-177.

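### The pilot's planning effect sizes get confidence intervals from a two-sample t-test that makes no allowance for therapy group, although sets of 6 are randomised, so the intervals overstate precision if outcomes cluster by group

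*Combined protocol and SAP*

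**What the plan says.** All references are to the combined protocol and SAP.

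- **Participants, Inclusion Criteria:** "We will enroll 60 veterans with PTSD".
- **Randomization Procedures:** "randomization will be implemented at the group level". The text then explains that "after 6 participants are recruited, they will be randomly assigned using urn randomization procedures, to either the TREC group or the MBSR group".
- **Data Analyses, Primary Aim 1 Hypothesis 1.1:** the mixed model allows for this. "Subject will be the clustering factor and it will be nested within therapy group which will also be considered random". Hypothesis 1.2 and Secondary Aim 1 Hypothesis 1.1 follow the same strategy.
- **Sample Size and Power Considerations, planning effect sizes:** "Effect sizes for determining the sample size for the larger RCT will be calculated based on differences between the baseline and post-treatment scores" on the STAXI-2 and BPAQ, and on difference scores for heart rate, skin conductance and emotion regulation. The next sentence is "Comparisons will be made using a two-sample t-test". One of two named safeguards against an inaccurate pilot estimate is "accounting for the effect size uncertainty by constructing confidence intervals around the observed effect size".
- **Same section, clustering:** the plan expects that "a portion of the variance in treatment effects will be accounted for by clustering of effects within a particular group". It then uses rho in a sample-size formula. It gives no value for rho and does not carry rho into the pilot intervals.

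**The concern.** The plan uses two variance models for the same data. The hypothesis tests treat the therapy group as a source of random variation. The effect-size step, on its natural reading, treats 60 people as 60 independent observations. Members of a group share sessions and a leader, and they were allocated together, so the independent information about treatment lies mainly between the 10 groups.

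This matters because the plan describes informing a later full-scale trial as the pilot's basic purpose and concedes that 60 may be too few for significance. The interval is meant to show how uncertain the pilot effect size is. If it ignores the randomised unit, it shows less uncertainty than there is.

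**Working it through.** The plan states no interval width, SD, power or rho for this step, so there is no figure of its own to reproduce.

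**Inputs from the documents**
- Total enrolled: 60. Set size: 6. Randomised units: 60 / 6 = 10.
- Comparison method: two-sample t-test. No group term is mentioned.

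**Assumptions**
- An even split by the urn: 5 groups (30 people) per arm.
- Full groups of 6 with no attrition.
- A 95% level, since the plan names none.
- rho of 0.01, 0.05 and 0.10. This is the intra-class correlation of the score being compared (for example, baseline-to-post change), not of a raw score at one visit.
- Results are for the mean difference with the SD set to 1. The small extra uncertainty from estimating the SD is left out of both intervals.

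**Step 1: the t-test interval.** df = 60 − 2 = 58.
Half-width = t(0.975, 58) × √(2/30) = 2.002 × 0.2582 = 0.517 SD, whatever rho is.

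**Step 2: the interval that respects the groups.** df = 10 − 2 = 8. Design effect = 1 + (6 − 1) × rho.
Half-width = t(0.975, 8) × √(2/30) × √(design effect) = 2.306 × 0.2582 × √(design effect).

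| Assumed rho | Design effect | Effective N (60 / design effect) | Half-width, 8 df | Ratio to 0.517 |
|---|---|---|---|---|
| 0.01 | 1.05 | 57.1 | 0.610 | 1.18 |
| 0.05 | 1.25 | 48 | 0.666 | 1.29 |
| 0.10 | 1.50 | 40 | 0.729 | 1.41 |

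**Step 3: separate the two parts.** The change of degrees of freedom alone gives 2.306 / 2.002 = 1.152, about 15 points of widening at any rho. The design effect multiplies that by √1.05 = 1.025, √1.25 = 1.118 or √1.50 = 1.225.

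**Step 4: coverage.** In a simulation of 100,000 trials per value of rho (5 groups of 6 per arm), the nominal 95% individual-level t interval covered the true difference as follows:
- rho = 0: 95.2%, so no deficit
- rho = 0.01: 94.5%
- rho = 0.05: 92.0%
- rho = 0.10: 89.1%

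A t interval on the group means (8 df) covered 94.9% to 95.1% for rho from 0 to 0.20.

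**Step 5: smaller groups.** At rho = 0.10, with the same two t quantiles:
- 5 members: √1.40 × 1.152 = 1.36
- 4 members: √1.30 × 1.152 = 1.31

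Both are below the 1.41 for full groups, so attrition reduces the gap.

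**The case against.** Several points on the other side stand.

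- **The link is inferred.** The plan does not say that the t-test is run on individuals, and it names no interval method, level or degrees of freedom; the 58 df is deduced. But the t-test is the only comparison method named there and no group-level summary is mentioned, so this is the natural reading. On any other reading the method is unspecified.
- **The size depends on rho, which the documents do not give.** At 0.01 the loss of coverage is trivial, and at zero the t-test is valid. What the plan does supply is the expectation that clustering will account for some variance. That fixes the direction but not the amount.
- **Not all of the widening measures error in the t-test.** The 15 points from the degrees of freedom appear even at rho = 0, where the t-test's coverage is correct. Coverage is the better measure of harm.
- **Clustering is not ignored elsewhere.** Hypothesis 1.1 and the analyses that follow its strategy model therapy group. The intervals are also not the only safeguard, since clinician consultation is the other.

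A reader might infer that the full trial will be mis-sized. The documents do not show this. With equal groups, ignoring clusters leaves the mean difference unbiased. The plan adds a separate clustering step when it turns to sample size, and it does not say how the interval limits would enter the sizing. Equally, that later step does not cure the pilot interval, because it acts on a sample size and not on the uncertainty of the estimate.

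**Conclusion.** The point holds for the planning effect-size intervals and no further. As written, on the natural reading, these intervals are too narrow whenever rho exceeds zero, and the plan itself expects that it will. For rho between 0.01 and 0.10, the nominal 95% interval covers about 94.5% down to 89%, and the appropriate half-width is 0.61 to 0.73 SD in place of 0.52 SD. These figures assume 5 full groups of 6 per arm and a 95% level.

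A reader might also take this to mean that the effect estimates are biased or that the trial's hypothesis tests are invalid. Neither follows: the fault is overstated precision in one planning step, and the tests already carry a random therapy-group term. For that reason it is a should-fix and not a must-fix.

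**What to change.** In Sample Size and Power Considerations, replace the two-sample t-test sentence. Take each planning effect size and its confidence interval from one of:

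- the mixed model of Hypothesis 1.1, with therapy group random and group-level degrees of freedom (about 8), keeping the group term and those degrees of freedom even if the group variance is estimated as zero; or
- a comparison of the group means (10 if all groups are formed, 8 df).

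State the confidence level, and report rho with its own interval for each measure.

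The cost is a wording change. It needs no new data, participants or procedures, because the model is already in the plan. The downside is that the reported intervals become wider.

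Three further suggestions are optional and do not follow from the clustering point: adjusting for baseline in place of raw change scores, stating which SD standardises each effect, and adding the Taylor Reaction Time Task, a primary outcome in Table 1, to the effect-size list.

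### The clustering formula for the future trial is an effective-sample-size expression presented as a required sample size, so as defined it gives the wrong number and falls as clustering rises

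*Combined protocol and SAP*

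**What the plan says.** All of this is in Sample Size and Power Considerations unless stated.

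- **Purpose.** The section presents the pilot chiefly as a source of planning information, and says that "the pilot RCT data will be used in power calculations to calculate the sample size for a later full-scale RCT".
- **Source of clustering.** Because treatment is given in groups, "a portion of the variance in treatment effects will be accounted for by clustering of effects within a particular group". The intra-class correlation ρ is "defined as the ratio of variance due to the clustering variable relative to the total variance (cluster and error").
- **Rule.** The plan says: "Once ρ has been determined, the adjusted sample size can be determined using the following formula". The expression it then gives is m = n × N / (1 + (n − 1)ρ).
- **Result.** Of the left-hand side, the plan says that "m is the effective number of independent observations after accounting for interclass correlation".
- **Inputs.** The two quantities on the right are defined separately: "n is the number of repeated measures per group; and N is the base sample size needed to detect the effect".
- **Group size.** Under Randomization Procedures, "after 6 participants are recruited, they will be randomly assigned using urn randomization procedures" to one arm or the other, so a therapy group has 6 members.

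No value is given for ρ, for N or for the future trial's size, and no other section offers a different clustering adjustment.

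**The concern.** The paragraph uses one symbol for two different quantities. A required sample size is what must be recruited so that the trial carries enough information; it rises with clustering. An effective sample size is the information that a given number of clustered participants carries; it falls with clustering. Here m is introduced as the first and defined as the second, while N is defined as a requirement, which belongs only to the first.

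The unit of n is also wrong for the purpose. The clustering described is of participants within a therapy group, but n is defined by repeated measures.

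This is the only rule in the plan for carrying the pilot's results over to a group-delivered trial. Applied as written, it would give the later trial a wrong size.

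**Working it through.** **Inputs**

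- Formula and definitions: final paragraph of Sample Size and Power Considerations.
- Cluster size n = 6: Randomization Procedures.
- Pilot of 60, hence 60/6 = 10 groups: Inclusion Criteria and Randomization Procedures.
- Base requirement N = 128 in total: an assumption (standardised difference 0.5, two-sided 5% level, 80% power). It sets only the scale; the ratios below do not depend on it.
- ρ: not given, so a range is shown.

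The plan states no figure to reproduce, so the formula itself is checked.

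**Step 1. Limits, with no assumed values**

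Write D = 1 + (n − 1)ρ for the design effect. The written rule is nN/D. The required total, if N suffices under independence, is N × D.

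- At ρ = 0, D = 1. The rule returns nN; the requirement is N.
- At ρ = 1, D = n. The rule returns N; the requirement is nN.
- For n > 1, D rises with ρ, so nN/D falls throughout while N × D rises.

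**Step 2. Where the two agree**

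nN/D = N × D when D = √n, that is ρ = (√n − 1)/(n − 1) = 1/(√n + 1). For n = 6 this is 1/3.449 = 0.29. Below it the rule oversizes; above it the rule undersizes. The ratio of written to required size is n/D².

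**Step 3. Numbers for N = 128, n = 6**

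| ρ | D | Written: 768/D | Required: 128 × D | Ratio: 6/D² |
|---|---|---|---|---|
| 0 | 1.00 | 768 | 128 | 6.00 |
| 0.05 | 1.25 | 614 | 160 | 3.84 |
| 0.10 | 1.50 | 512 | 192 | 2.67 |
| 0.20 | 2.00 | 384 | 256 | 1.50 |
| 0.30 | 2.50 | 307 | 320 | 0.96 |
| 0.50 | 3.50 | 219 | 448 | 0.49 |
| 1 | 6.00 | 128 | 768 | 0.17 |

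At ρ = 0.50 the 219 participants carry the information of 219.4/3.5 = 62.7 independent ones. The expected z statistic is 0.5 × √(62.7/4) = 1.98 against a critical value of 1.96, so power is about 50%.

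**Step 4. n taken literally as repeated measures**

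Table 1 has the self-report outcomes on five occasions. With n = 5 the rule gives 640/1.2 = 533 at ρ = 0.05 and 640/1.4 = 457 at ρ = 0.10, against the same 160 and 192 for groups of 6. The result is still far too large and still falls with ρ.

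**Step 5. The reading under which the expression is valid**

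Let N be the number of groups and n the participants per group. For the pilot, 10 groups of 6 give m = 60/D: 60 at ρ = 0, 48 at ρ = 0.05, 40 at ρ = 0.10. These are correct effective sizes.

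To get a requirement from this, set m = 128 and solve for the number of groups, 128 × D/6. That is 26.7 groups (160 participants before rounding up to whole groups) at ρ = 0.05, and 32 groups (192) at ρ = 0.10. These match the required column in Step 3.

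**The case against.** The strongest defence is that the expression is sound and only its labels are wrong. The plan does define m as an effective number of observations, and such a number should fall as ρ rises. With N as the number of groups and n as members per group, n × N is simply total participants, and Step 5 recovers the right requirement. The phrase about repeated measures may be loose wording for observations per cluster. This stands as an account of how the error probably arose. It does not rescue the text: it contradicts the stated definition of N, and it needs a solving step that the plan does not give.

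A second objection also has force: no number in the plan is wrong, because none is given. Harm depends on someone later applying the rule as written, and a result of n times the base size at ρ = 0 would be conspicuous.

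Two stronger readings are tempting, and the documents do not support them.

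- A reader might infer that, because the rule falls with ρ, the future trial would be underpowered. For groups of 6 that is so only above ρ of about 0.29. At ρ of 0.05 or 0.10 the error is a grossly oversized trial.
- A reader might infer that the pilot's main product is compromised. The section also plans effect sizes with confidence intervals and consultation with clinicians, and neither uses this formula. Enrolment of 60 and the mixed model with a random therapy-group term (Data Analyses, Primary Aim 1, Hypothesis 1.1) are untouched.

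**Conclusion.** The rule is wrong as written. That conclusion rests on algebra alone: with the plan's definitions it returns n × N when no adjustment is needed, and it moves opposite to the true requirement.

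The size of the error rests on assumptions: N = 128, groups of 6 of equal size, and the same ρ in both arms. On these the rule asks for 3.8 times the required number at ρ = 0.05, 2.7 times at ρ = 0.10, and about half at ρ = 0.50. A different N scales both columns equally; a different group size moves the crossover.

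The fault is confined to the clustering step for the later trial and takes effect only if the rule is applied literally. It should be fixed, but it does not put the present trial in question.

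**What to change.** Replace the formula and its definitions in the final paragraph of Sample Size and Power Considerations by one of two equivalent forms.

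1. N_adjusted = N × [1 + (n − 1)ρ], where N is the total required under independence and n is the planned number of participants per therapy group.
2. Keep m = nN/(1 + (n − 1)ρ) as the effective sample size, redefine N as the number of therapy groups and n as participants per group, and state that the number of groups is found by setting m equal to the base requirement and rounding up.

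In either case, stop using one symbol for both the adjusted and the effective size, and remove the reference to repeated measures. Computing the adjusted size over a range of ρ would be a useful option, but the correction does not depend on it.

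The cost is one paragraph of wording. No participant, visit, procedure or pilot analysis changes.
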